7.3.2.2. Additional analyses for efficacy

This section summarizes the additional analyses as compared to the protocol defined analyses (described in section 7.3.1.6).

204889 (Malaria-094) Statistical Analysis Plan

Table 6 Incremental efficacy analyses against all episodes of clinical malaria.

Risk Period (months)	Full dose groups, control	Fractional dose groups, ontrol			Objectives	
		Fx012- 14	Fx017-20	Control	_	
Exposed set			1	ı		
D0-M20	R012-20	Х			Prolonged follow-up period for	
D0-M26 D0-M32 D0-M38	R012-14	Х			primary objective	
D0-M50	R012-20	х			 Prolonged follow-up period for primary objective 	
	R012-14	Х	Χ		Prolonged follow-up period for	
	-	х	Х		 primary objective To compare a delayed factional dose schedule with early fractional- and early full dose schedule 	
Per protocol s	set			·		
M1-M7	Control		Х		VE of delayed fractional third dose	
M2.5-M20	R012-20	Х		Х	Prolonged follow-up period for	
	R012-14			Х	primary objective	
	Control	Х			Vaccine efficacy of early	
	R012-20 vs R012- 14				 fractional/full dose schedule Incremental efficacy of full dose (standard schedule versus early booster) schedule 	
M2.5-M26	R012-20	Х		Х	Prolonged follow-up period for	
M2.5-M32	R012-14	Х		Х	primary objective	
M2.5-M38	Control	Х			Vaccine efficacy of early	
M2.5- M50	R012-20 vs R012- 14				 fractional/full dose schedule Incremental efficacy of full dose (standard schedule versus early booster) schedule 	
M7.5-M26 M7.5-M32 M7.5-M38 M7.5-M50	Control		х		VE of delayed fractional third dose at prolonged follow-up periods	
M14-M20	R0-12-14	Х		Х	 Incremental efficacy 6 months 	
M26-M32	Control	X			post dose 4 and 5 (fractional vs full dose) • VE 6 months post dose 4 and 5 of early fractional- and full dose schedule	
M14-M26	R0-12-14			Х	VE 12 months post dose 4, 5 and	
M26-M38 M38-M50	Control	Х			6 of the early fractional- and full dose schedule	
M20-M32	R012-20			Х	VE 12 months post dose 4 of standard full dose schedule	
M32-M50	Control		х		VE 18 months post dose 5 of fractional delayed schedule	

X=group comparisons

Table 7 Incremental efficacy analyses against first or only episodes of incident infection

Risk Period (months)	Full dose groups, control	Fractional dose groups, control				ups,	Objectives
		Fx012- 14	Fx017-20	Control			
Exposed set			•				
D0-M20	R012-20	Х			Prolonged follow-up period for		
	R012-14	Х			primary objective		
Per protocol s	et						
M1-M7	Control		Х		VE of delayed fractional third dose		
M2.5-M20	R012-20	Х		Х	Prolonged follow-up period for		
	R012-14			Х	primary objective		
	Control	Х			Vaccine efficacy of early		
	R012-14 vs R012-				fractional/full dose schedule		
	20				Incremental efficacy of full dose		
					(standard schedule versus		
					early booster) schedule		
M14-M20	R012-14	Χ		Х	 Incremental efficacy 6 months 		
	Control	Х			post dose 4 (fractional vs full dose)		
					VE 6 months post dose 4 of early fractional- and full dose		
					schedule		

X=group comparisons

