1.2.1. Rationale for the study design

A recent CHMI study (MALARIA-071) ***demonstrated superior protection against malaria infection*** associated with the use of a fractional third dose in a 0, 1, 7-month schedule with a vaccine efficacy against infection of 86.7% (95% CI: 66.8; 94.6; p<0.0001) versus 62.5% (95% CI: 29.4; 80.1; p=0.0009) in the standard 0, 1, 2-month schedule. The incremental efficacy of the 0, 1, 7-month schedule over the 0, 1, 2-month schedule was 64.4% (95% CI: -7.9; 88.3; p=0.0741) [Regules, 2016]. The current study intends to establish POC for a fractional dose schedule under conditions of natural exposure. The study will be conducted in children 5-17 months old at first vaccination living in areas of mid to high malaria transmission, in line with the age group recommended by the World Health Organization (WHO) [WHO, 2016]. Infants 6-12 weeks old will not be included in this POC study to avoid interference of co-administration with the standard Expanded Program on Immunization (EPI) vaccines.

Results from this study will be critical in informing future possibilities for the development of vaccine-based strategies which, in combination with other interventions, may contribute to the malaria elimination agenda.

The study proposed herein will include five study groups. One group (R012-20) will receive the standard schedule consisting of RTS,S/AS01_E full dose given at Month 0, Month 1, Month 2 and a fourth dose at Month 20. This corresponds to the schedule that received a positive scientific opinion from EMA. The four other groups will receive alternative schedules as follow:

- Group R012-14-mD will receive RTS,S/AS01_E full dose at Month 0, Month 1, Month 2, an early fourth dose at Month 14 and yearly full doses at Month 26 and Month 38.
- Group Fx012-14-mFxD will receive RTS,S/AS01_E full dose at Month 0 and Month 1, RTS,S/AS01_E fractional dose (1/5th dose) at Month 2 and yearly fractional doses at Month 14, Month 26, Month 38.
- Group Fx017-mFxD will receive RTS,S/AS01_E full dose at Month 0 and Month 1, RTS,S/AS01_E delayed fractional third dose (1/5th dose) at Month 7 and yearly fractional doses at Month 20 and Month 32.
- Control group: will receive three doses of rabies vaccine at Month 0, Month 1 and Month 2.

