6.1.3. Per-Protocol Set for analysis of efficacy (PPS for efficacy)

For the primary analysis up to month 14, the PPS for efficacy will include all subjects from the ES who fulfilled eligibility criteria and who received all vaccinations according to protocol procedures within the protocol specified intervals that contribute to the time at risk in the follow-up period starting 14 days post-Dose 3.

For the final analysis up to month 50, all subjects who have not received Dose 4 of study vaccine or subsequent yearly doses (Dose 5 and Dose 6) according to protocol will be censored at the last contact date prior to the first missed dose recorded and will contribute to the PPS analysis up to censoring.

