		vac6→ser10 (m50) is outside [+308-420 days]	
		• Fx017- 20:	
		vac2→ser2(M2) is outside [21-35 days]	
		vac3→ser4 (M8) is outside [21-35 days]	
		vac4→ser6 (M21) is outside [21- 35 days]	
		vac5→ser7 (M33) is outside [21- 35 days]	
		vac5→ser9 (M50) is outside [+476-616 days]	
2100	Serological results	All visits where serum samples are	Immunology
	not available post-	planned (see Table 1– time points for	
	vaccination if ALL are missing and subject in Immunogenicity	immunogenicity)	
2120	Subset	All vigits where some someles are	Immunalagy
2120	Incomplete assessment and mislabelling (sample	All visits where serum samples are planned (see Table 1– time points for immunog enicity)	Immunology
	tested/not tested) of		

Code	Condition under which the code is used	Visit (timepoints) where the code is applicable	Applicable analysis set
	blood sample, for specific assays		

Code	Condition under which the code is used	Visit (timepoints) where the code is applicable	Applicable analysis set
3100	Subjects without follow up data starting 14 days post dose 3 Note that subjects not receiving dose 4, 5 and 6 will be censored at the last contact prior to whichever first missed dose recorded	 Applies under following conditions: First 3 vaccinations are administered No data available 14 days after visit 4 for Control, R012-20, R012-14, Fx012-14 No data available 14 days after visit 10 for Fx017-20 	Efficacy
3200	Subjects not receiving first 3 doses	 Applies under following conditions For control, R012-20, R012-14, Fx012-14 → no vaccination administered at visit 2,3 and 4. For Fx017-20 → no vaccination administered at visit 2,3 and 10 	Efficacy

^{*}a Dynamic elimination approach will be used for the definition of the immunogenicity PPS (Analysis M21 E1_02, Analysis M33 E1_03, Final analysis). This means that for codes 1040, 1070, 1080,1090, 2080, only the data relevant/posterior to the deviation will be eliminated. For codes 2040, 2090, 2120, the data elimination will be visit specific. For the efficacy PPS subjects will be fully excluded based on the elimination codes. However, subjects included in the efficacy analysis could be censored at last contact date.

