[2½-14]	14 days post dose 3 of RTS,S or	Date of Month 14 visit – 1 or drop out date from	Primary objective: Fx012-14 vs R012-20 +R012-14	First or only- and all episodes	First or only episode
	control vaccine (day of dose 3	study conclusion, whichever occurs	Fx012-14 vs control	First or only- and all episodes	First or only episode
	vaccination + 14)	first	R012-20 +R012-14 vs control	First or only- and all episodes	First or only episode
-	months post dos	e 2 and 3: groups versus contro	ols		
[2½-9]	14 days post dose 3 of RTS,S or	Date of Month 9 visit – 1 or drop out date from	R012-20+ R012-14 vs Control	First or only- and all episodes	First or only episode
	control vaccine (day of dose 3 vaccination +	study conclusion, whichever occurs first	Fx012-14 vs control	First or only- and all episodes	First or only episode

204889 (Malaria-094) Statistical Analysis Plan

Risk Period (months)	Start of risk period (at subject level)	End of risk period (at subject level)*	Group comparisons	Clinical Malaria	Incident infection
[7½-14]	14 days post dose 3 of RTS,S or control vaccine (day of dose 3 vaccination + 14)	Date of Month 14 visit – 1 or drop out date from study conclusion, whichever occurs first	Fx017-20 vs control	First or only- and all episodes	First or only episode
[1-7]	Day of second vaccination of RTS,S or control vaccine	Date of Month 14 visit – 1 or drop out date from study conclusion, whichever occurs first	Fx017-20 vs control	First or only- and all episodes	First or only episode

Analyses up to 38 months after dose 3:

- incremental of fractional dose versus full dose
- vaccine efficacy of all groups versus controls

[2½-20]	14 days post dose 3 of	Date of Month 20 visit – 1 or drop	Fx012-14 vs control	All episodes	First or only episode
	RTS,S or control vaccine	out date from study conclusion,	R012-14 vs control	All episodes	First or only episode
	(day of dose 3 vaccination +	whichever occurs first	R012-20 vs control	All episodes	First or only episode
	14)		Fx012-14 vs R012-20	All episodes	First or only episode
			Fx012-14 vs R012-14	All episodes	First or only episode
			R012-20 vs R012-14	All episodes	First or only episode
[7½-19]	14 days post dose 3 of RTS,S or control vaccine (day of dose 3 vaccination + 14)	Date of Month 19 visit – 1 or drop out date from study conclusion, whichever occurs first	Fx017-20 vs control	All episodes	First or only episode
[2½-26]	14 days post	Date of Month 26/	R012-14 vs control	All episodes	NA

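### The Month 1–7 Fx017-20 versus Control analysis is labelled as efficacy of a third dose not yet given, and its per-protocol set conditions the two arms on later events unequally

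*SAP*

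**What the plan says.** SAP Section 7.3.2.2 lists analyses added to those in the protocol. Under the per-protocol heading, Tables 6 and 7 each have an M1–M7 row comparing Fx017-20 with Control, for clinical malaria and incident infection respectively. The objective in both is "VE of delayed fractional third dose". In Table 6 the same phrase opens the objective for the M7.5–M26 to M7.5–M50 windows, which do follow dose 3.

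Protocol Section 1.2.1 gives this group a "delayed fractional third dose (1/5th dose) at Month 7".

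SAP Section 7.3.2.1, Table 4, defines the [1-7] risk period. It starts on the "Day of second vaccination of RTS,S or control vaccine" and sits in a block headed as post dose 2 and 3. Its end is printed as "Date of Month 14 visit – 1 or drop out date from study conclusion, whichever occurs first".

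SAP Section 6.1.3 builds the efficacy per-protocol set on vaccinations "that contribute to the time at risk in the follow-up period starting 14 days post-Dose 3". Section 6.2.2 gives the exclusion codes:

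- Code 3200: "Subjects not receiving first 3 doses", with dose 3 at Visit 10 (Month 7) for Fx017-20 and Visit 4 (Month 2) for Control.
- Code 3100, Fx017-20: "No data available 14 days after visit 10 for Fx017-20".
- Code 3100, Control and the other groups: "No data available 14 days after visit 4 for Control, R012-20, R012-14, Fx012-14".
- Code 3080, the efficacy counterpart of code 2080: the first three doses must be on schedule. Dose 2 to dose 3 is 161–203 days in Fx017-20 and 21–35 days in Control.

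The footnote to that table reserves data-by-data elimination for the immunogenicity set. For efficacy, the whole subject is removed.

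**The concern.** Two things do not fit together. The label credits the estimate to a dose given only when the window closes, so a reader of the study report would take efficacy after two full doses for efficacy of the delayed fractional dose. Third-dose spacing is one of the trial's stated aims, so the confusion matters.

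The analysis set also depends on what happens after the window opens, and to a different extent in each arm. An Fx017-20 child who withdraws, dies or misses dose 3 between about Month 2.5 and Month 7.5 is deleted together with all earlier follow-up and episodes. A control child with the same history from Month 2.5 onward stays in. If leaving or missing dose 3 is related to malaria, the comparison is no longer protected by randomisation.

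**Working it through.** The documents give no sample size, power or expected estimate for this analysis, so there is no planned figure to reproduce. The check compares the window with the entry conditions, in days from dose 2, at the SAP's 30.5 days per month.

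**Window as titled.** Month 1 to Month 7: 6 × 30.5 = 183 days.

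**Day on which a child qualifies** = interval from dose 2 to dose 3, plus 14 days.

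| | Shortest allowed | Nominal | Longest allowed |
|---|---|---|---|
| Fx017-20 | 161 + 14 = 175 | 183 + 14 = 197 | 203 + 14 = 217 |
| Control | 21 + 14 = 35 | 30.5 + 14 = 44.5 | 35 + 14 = 49 |

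In Fx017-20 the titled window ends at the visit where dose 3 is given, so the whole window precedes the qualifying day, whatever the interval. In Control the conditioning covers 35/183 = 19% to 49/183 = 27% of the window, nominally 44.5/183 = 24%.

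**Window as printed in Table 4.** Month 1 to Month 14 is 13 months: 6/13 = 46% before dose 3 and 7/13 = 54% after it. It is then neither a two-dose nor a third-dose estimate, and the unequal entry conditions remain.

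**Illustration of possible bias (assumptions, not document figures).** Take a control rate of 0.5 per person-year (the planning value in Protocol Section 11.4), six months of follow-up and true efficacy v. Let q be the share of Fx017-20 excluded beyond any exclusion in Control, and R the ratio of exclusion risk in children with an episode to that in children without.

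- True risk: p = 1 − exp(−0.5(1 − v) × 0.5).
- Exclusion risk in children with an episode: e = Rq / (1 − p + Rp).
- Risk among those retained: p′ = p(1 − e)/(1 − q).
- Apparent efficacy: 1 − [−2 ln(1 − p′)]/0.5.

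For v = 0, p = 0.221. With q = 16.7% and R = 2, e = 0.273, p′ = 0.193 and apparent efficacy is 14%. Apparent efficacy when the truth is zero:

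| q | R = 0.5 | R = 1 | R = 2 | R = 3 |
|---|---|---|---|---|
| 5% | −3% | 0% | 4% | 6% |
| 10% | −6% | 0% | 8% | 13% |
| 16.7% | −10% | 0% | 14% | 24% |

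The last row uses (300 − 250)/300, the overall non-evaluable share implied by Protocol Section 11.4. With v = 30% and q = 16.7%, the four values are 23%, 30%, 41% and 49%. The sign depends entirely on R, which the documents do not give.

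**The case against.** **The analysis set may be meant differently.** Section 6.1.3 is framed for the primary analysis, and its reference to vaccinations contributing to time at risk might be read as requiring only doses 1 and 2 here. The codes are also loosely drafted: 3200 describes children with no vaccination at three named visits, and 3080 cites Visit 7 for Fx017-20 where dose 3 is at Visit 10. These look like slips. But the sentence in Section 6.1.3 ties the set to follow-up after dose 3, and neither the codes nor the footnote makes an exception for this window. As written, the restriction applies.

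**Table 4 is partly right.** It starts the period at dose 2 under a heading that mentions dose 2, so the mislabelling is confined to the objectives in Tables 6 and 7. That stands. The printed Month 14 end softens the label point if taken literally, but it contradicts the row's own title.

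**Other analyses cover some of this ground.** Fx017-20 versus Control over D0–M14 is planned in the exposed set, and Section 7.3.2.6 plans piecewise Cox models in six-month periods without naming a set. Neither isolates M1–M7, and Table 3 has no exposed-set version of this window.

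**Little depends on it.** Under SAP Section 8 only the primary comparison and the 12-month comparison of the Month 7 fractional schedule with three full doses are tested in sequence. Everything else is descriptive. That is correct and limits the weight of the point.

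**A febrile child is not simply dropped.** A reader might infer that fever at the Month 7 visit removes children because of malaria. Protocol Sections 6.6.14 and 7.5 allow rescheduling within the permitted interval, which runs to 203 days, about 20 days beyond the six-month target. Only illness outlasting that interval, or withdrawal at the investigator's discretion, leads to exclusion by this route.

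**Conclusion.** The point holds on two counts that need no assumption. The label in Tables 6 and 7 is wrong for the window as titled. The entry conditions are also unequal: about 197 days after dose 2 in Fx017-20 against about 44.5 days in Control. The Table 4 end date is a separate contradiction in the same row.

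Three stronger readings are not supported:

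- *Selection in one arm only.* Controls are also conditioned on dose 3 and on data 14 days later, both after the Month 1 start. The difference is one of extent.
- *Efficacy is inflated.* That would require excluded Fx017-20 children to have more malaria than those retained. The documents do not say so; under the opposite assumption efficacy is understated, and with no association there is no bias.
- *A numerical size for this trial.* Neither the share excluded nor its link to malaria is given. The planning rate of 0.29 per person-year describes the standard three-dose schedule, not two doses over Months 1–7. The table above shows only what could happen under stated assumptions.

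This is a correction worth making to an added, descriptive analysis. It affects neither the primary test nor the sequentially tested secondary comparison.

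**What to change.** 1. In Tables 6 and 7, relabel the M1–M7 row as efficacy after two full doses, before dose 3.
2. Define the analysis set for this row by eligibility and in-window doses 1 and 2 only, with the same rule in both arms, and state that codes 3100, 3200 and the dose 3 part of 3080 do not apply. Alternatively, use the exposed set as SAP Section 6.1.2 defines it, that is, by the treatment actually received; analysing it by randomised group would conflict with that definition.
3. In Table 4, correct the end of the [1-7] period to the day before the Month 7 visit (or drop-out if sooner). Without this change the new label would be false. Both arms have a scheduled Month 7 contact: a clinic visit for Fx017-20 and a field-worker visit for Control.

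The cost is SAP wording and one population flag. No new data are needed.

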1.2. Rationale for the study

GSK Biologicals and PATH are committed to develop a malaria vaccine for reduction of malaria disease burden in children and contribution to the malaria elimination goal. Characterization of an optimal dosing regimen and boosting schedules will be critical.

The results of the efficacy study MALARIA-055 PRI, including the long term follow-up data and efficacy of the fourth dose administered 18 months after the third dose, and the preliminary results of MALARIA-071 were reviewed by the European Medicines Agency (EMA) during the assessment of the initial Application of the RTS,S/AS01_E candidate vaccine. The EMA asked the company to address the following points in ongoing or future studies: 1) the timing of the fourth dose and evaluation of the safety and efficacy of an early fourth dose; 2) the efficacy and safety of multiple yearly doses and whether the vaccine predisposes to some degree of hyporesponsiveness to sequential doses; and 3) the plans to further investigate the potential utility of a delayed and fractionated third dose schedule in the target age range.

The current study is designed to address these points in the pediatric population. It aims to:

- Establish proof-of-concept (POC) for a fractional (Fx) dose schedule under conditions of natural exposure.
- Establish the role of third dose spacing in a fractional dose schedule.
- Describe the effect of an earlier full fourth dose at Month 14.
- Describe the effect of multiple fractional or full yearly doses.

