2. **Risk mitigation.** Subjects will have access to the best locally available malaria prevention and treatment options. All screened subjects will be provided with an insecticide-treated bednet (ITN), and malaria diagnosis and treatment will be ensured. The investigator will make every effort to ensure that preventive measures as provided by the government are adhered to and under circumstances where this is not possible discussions with the sponsor need to take place. It is anticipated that subjects will benefit from participation in the study in terms of facilitated access to care and relatively intense health monitoring. Reduced levels of morbidity related to participation in a RTS,S/AS01_E study has been documented [[Hamel, 2014](#)].
3. **Study design justification.** Without a control group, the following scientific questions could not be answered with scientific integrity:
 - Comparison of malaria incidence between different time periods.
Without a control group, the direct comparison of post-RTS,S/AS01_E vaccination malaria incidence between two different study periods (example: assessment of post-Dose 3 protection in the 0, 1, 2-month and 0, 1, 7-month schedules, evaluation of optimal timing of the fourth dose, waning of efficacy) would carry a risk of bias associated with seasonal variations in malaria incidence.
 - Evaluation of strain-specificity of protection.
A genetic characterization of malaria infections is planned as an ancillary study (using samples collected in the present study) with the aim to determine whether vaccine efficacy varies according to the parasite strain. This requires comparison of parasite genetics in the vaccinated groups with the Control group.
4. **Public health need.** RTS,S/AS01_E has been shown to prevent malaria with a moderate level of efficacy [[The RTS,S Clinical Trials Partnership, 2015](#)]. The development of a malaria vaccine with higher efficacy remains an important public health need [[Malaria Vaccine Technology Roadmap, 2013](#)]. Finding the immunization schedule able to provide the highest protection is very relevant to local public health needs.

To be noted, the study subjects in the Control group will get the benefit of receiving a rabies vaccine as comparator vaccine, also advocated as a valuable preventive health intervention by the WHO [[WHO, 2007](#)].

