[2½-32]	dose 3 of	32/38/50 visit – 1	Fx012-14 vs control	All episodes	
[2½-38] [2½-50]	RTS,S or control vaccine	or drop out date from study	R012-20 vs control	All episodes	
[2/2-50]	(day of dose 3	conclusion,	Fx012-14 vs R012-20	All episodes	
	vaccination +	whichever occurs	Fx012-14 vs R012-14	All episodes	
	14)	first	R012-20 vs R012-14	All episodes	
[7½-26] [7½-32] [7½-38] [7½-50]	14 days post dose 3 of RTS,S or control vaccine (day of dose 3 vaccination + 14)	Date of Month 26/32/38/50 visit – 1 or drop out date from study conclusion, whichever occurs first	Fx017-20 vs control	All episodes	NA

Risk Period (months)	Start of risk period (at subject level)	End of risk period (at subject level)*	Group comparisons	Clinical Malaria	Incident infection
Analyses po	ost booster dose	(post dose 4, 5 and	6):		
[M14-M20]	Day of fourth RTS,S dose or	Date of Month 20 visit – 1 or drop	Fx012-14 vs R012-14	All episodes	First or only episode
	month 14 visit for control	out date from study conclusion,	R012-14 vs control	All episodes	First or only episode
		whichever occurs first	Fx012-14 vs control	All episodes	First or only episode
[M14-M26] [M26-M32]	Day of fourth/fifth/sixth	Date of Month 26/32/38/50 visit –	Fx012-14 vs R012-14	All episodes	NA
[M26-M38]	RTS,S dose or	1 or drop out date	R012-14 vs control	All episodes	
[M38-M50]	month 14/26/38 visit for control	from study conclusion, whichever occurs first	Fx012-14 vs control	All episodes	
[M20-M32]	Day of fourth	Date of Month 32	Fx017-20 vs R012-20	All episodes	NA
	RTS,S dose or month 20 visit	visit – 1 or drop out date from	Fx017-20 vs Control	All episodes	
	for control	study conclusion, whichever occurs first	R012-20 vs Control	All episodes	
[M32-M50]	Day of fifth RTS,S dose or M32 visit for control	Date of Month 50 visit – 1 or drop out date from study conclusion, whichever occurs first	Fx017-20 vs Control	All episodes	NA

^{*} if visit date and last contact date are both missing then subjects will be censored at month [x] times 30.5 days post dose 2/3/4/5/6.

Table 5 Risk periods for clinical Malaria & incident infection for the per protocol set: Comparisons with unequal calendar time

Risk Period (months)	Start of risk period (at subject level)	Stop (maximum)*	Group comparisons	Clinical Malaria	Incident infection
Analyses 6 m	onths post dose	3: fractional dose versu	s full dose		

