10. CHANGES FROM PLANNED ANALYSES

The Total Vaccinated Cohort and the According To Protocol cohort have been renamed Exposed Set (ES) and Per-Protocol Set (PPS) respectively.

The seropositivity threshold for anti-CS has been updated from 0.5 EU/ml to 1.9 EU/ml.

A Solicited Safety Set has been added in the analysis set section to fit with the new statistical rules and layouts applicable from the 12th of November 2018.

For purposes of analyses and to simplify the naming convention of the groups in Figure 1 haven been simplified. The label names of the study groups have been renamed according to the following table:

Vaccination schedule	Group label in protocol	Group label in SAP
RTS,S/AS01 _E full dose given at Month 0, Month 1, Month 2 and a fourth dose at Month 20	R012-20	R012-20
RTS,S/AS01 _E full dose at Month 0, Month 1, Month 2, an early fourth dose at Month 14 and yearly full doses at Month 26 and Month 38	R012-14-mD	R012-14
RTS,S/AS01 _E full dose at Month 0 and Month 1, RTS,S/AS01 _E fractional dose (1/5 th dose) at Month 2 and yearly fractional doses at Month 14, Month 26, Month 38	Fx012-14-mFxD	Fx012-14
RTS,S/AS01 _E full dose at Month 0 and Month 1, RTS,S/AS01 _E delayed fractional third dose (1/5 th dose) at Month 7 and yearly fractional doses at Month 20 and Month 32	Fx017-mFxD	Fx017-20
Rabies vaccine at Month 0, Month 1 and Month 2	Control	Control

A sequential approach to the analysis of incremental efficacy over the 12-month period post-dose 3 of a schedule with a fractional dose at month 7 versus 3 full doses was implemented (see section 8).

204889 (Malaria-094) Statistical Analysis Plan

The following analyses were added or modified:

- Unsolicited adverse events within 7 days after each vaccination will be described in addition to the 30 days analysis
 - Analyses on the occurrence of PIMDs (described in section Secondary endpoints) were added in section Analysis of safety and reactogenicity planned in the protocol, as they were missing in the protocol
- Secondary endpoint for efficacy
 - Analyses considering different calendar follow-up time was updated. In the protocol an indirect comparison was suggested taking into account incidence in controls, while for the SAP another proposal is suggested as described in section 7.3.1.1
 - Analysis of incident infection will only be performed up to M20 since infection with *P. falciparum* was regularly (monthly) evaluated until this time point.

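### Every planned direct comparison of R012-14 with R012-20 starts at Month 2.5 and none at Month 14, so the relative effect of the early fourth dose is diluted

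*SAP*

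**What the plan says.** Protocol 1.2 gives as its third aim "Describe the effect of an earlier full fourth dose at Month 14". The same section records that the regulator asked about the timing of the fourth dose and the efficacy of an early one. Protocol 1.2.2 also names "evaluation of optimal timing of the fourth dose, waning of efficacy" among its examples of questions that compare study periods and so need a control group.

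SAP section 10 sets out the two full-dose schedules. R012-20 has "full dose given at Month 0, Month 1, Month 2 and a fourth dose at Month 20". R012-14 has the same first three doses, then "an early fourth dose at Month 14 and yearly full doses at Month 26 and Month 38". The two arms are pooled up to Month 14 for the primary analysis.

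The direct contrasts of these arms are as follows.

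- SAP Table 4 (per protocol set) lists "R012-20 vs R012-14" over M2.5-M20, for all episodes of clinical malaria and for first or only incident infection. It repeats the pair over M2.5 to M26, M32, M38 and M50 for all episodes of clinical malaria.
- SAP Tables 6 and 7 repeat these rows and give their purpose as "Incremental efficacy of full dose (standard schedule versus early booster) schedule".
- SAP Table 3 (exposed set) and the analysis list in Protocol 11.7.6 contain no such contrast.

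The post-booster rows of Table 4 that begin at Month 14 start time at risk at the fourth dose or at the "month 14 visit for control". Their pairs are Fx012-14 versus R012-14, "R012-14 vs control", and Fx012-14 versus Control. R012-20 enters a post-booster row only for M20-M32.

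**The concern.** Before Month 14 the two arms cannot differ except by chance. Between Month 14 and Month 20 one arm has had its fourth dose and the other has not. That is the only stretch that isolates giving the dose early, and no direct comparison is confined to it. The row whose stated purpose is standard schedule versus early booster averages that stretch with 11.5 months of identical treatment.

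A rate ratio close to 1 from that row could be read as little benefit from the early dose when it mostly reflects shared follow-up. The regulator's first question would then be answered by an estimate of a different and smaller quantity.

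**Working it through.** **Inputs.** Protocol 11.4 gives 250 evaluable children per group, 0.29 episodes per person-year in the standard-schedule groups and 0.16 in the fractional group. The windows come from SAP Tables 4 and 6. The documents give neither the time course of incidence nor an expected effect of the early dose, so both are assumed below. Counts are taken as Poisson; overdispersion would lower every z and power.

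**The plan's own figure.** No power is stated for R012-14 versus R012-20. The stated figure, at least 90%, is for the primary comparison.
- Expected first events over 11.5 months: 500 × (1 − exp(−0.29 × 11.5/12)) = 121.3 and 250 × (1 − exp(−0.16 × 11.5/12)) = 35.5.
- With hazard ratio 0.16/0.29 = 0.552 and 2:1 allocation, Schoenfeld's formula gives 94%. A two-proportion formula gives 91% and a Wald test 88%.
- The stated power is therefore broadly reproduced, and the same inputs are used below.

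**Dilution over M2.5-M20, all episodes.** Let r be the true reduction over M14-M20, and k the R012-20 incidence in M14-M20 divided by that in M2.5-M14. The reduction seen over the whole window is r × w, with w = 6k / (11.5 + 6k).

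| k | w | Dilution (1/w) |
|---|---|---|
| 0.5 | 0.207 | 4.8-fold |
| 1 | 0.343 | 2.9-fold |
| 2 | 0.511 | 2.0-fold |
| 3 | 0.610 | 1.6-fold |

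**Size at k = 1.** Expected R012-20 episodes are 250 × 0.5 × 0.29 = 36.25 over M14-M20, and 250 × (17.5/12) × 0.29 = 105.7 over M2.5-M20. For r = 40%:
- M14-M20: 36.25 versus 21.75; z = ln(36.25/21.75) / √(1/36.25 + 1/21.75) = 0.511/0.271 = 1.88.
- M2.5-M20: 105.7 versus 91.2; z = ln(105.7/91.2) / √(1/105.7 + 1/91.2) = 0.148/0.143 = 1.03.

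| True reduction M14-M20 | Seen over M2.5-M20 | Power M14-M20 | Power M2.5-M20 |
|---|---|---|---|
| 30% | 10.3% | 28% | 12% |
| 40% | 13.7% | 47% | 18% |
| 50% | 17.1% | 67% | 26% |

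**Longer windows.** M14-M20 is 6/23.5 = 25.5% of M2.5-M26, and R012-20 receives its own fourth dose at Month 20. At constant underlying incidence, a 30% benefit over M14-M20 becomes 1 − (11.5 + 4.2 + 6)/23.5 = 7.7% if the arms are equal over M20-M26. It becomes 1 − (11.5 + 4.2 + 7.8)/23.5 = 0% if R012-14 then has a 30% higher rate. Windows ending after Month 26 also include R012-14's fifth dose, and those ending after Month 38 its sixth.

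**First or only incident infection, M2.5-M20 (Table 7).** Children infected before Month 14 no longer contribute. At a constant rate λ, the share of first events falling after Month 14 is (exp(−λ × 11.5/12) − exp(−λ × 17.5/12)) / (1 − exp(−λ × 17.5/12)). Its inverse, an approximate dilution factor, is 3.4 at 0.29 per year and 5.1 at an assumed 1 per year.

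**The case against.** The case for the plan has real substance.

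- **The aim is only to describe, and control-referenced rows exist.** R012-14 versus Control is planned over M14-M20 and M14-M26, and R012-20 versus Control over M20-M32. Protocol 1.2.2 itself points to the Control group for timing of the fourth dose, and no formal objective names R012-14 versus R012-20. This stands as far as it goes. But R012-14 versus Control from Month 14 combines dose 4 with residual protection from doses 1 to 3, and no defined row gives R012-20 over the same months.
- **A reader might infer that R012-20 is not looked at between Month 14 and Month 20 at all.** The documents do not support that. SAP 7.3.2.6 plans 6-month piecewise Cox models of each arm versus Control, SAP 7.3.2.5 plans 3-monthly cases averted, and SAP 7.3.1.3 tabulates infection prevalence by arm at each monthly visit to Month 20. However, no cut-points are stated. If cut from Day 0, six-month periods (12-18, 18-24) would straddle both Month 14 and Month 20. None of these gives an arm-to-arm estimate with a confidence interval.
- **Dilution affects the ratio, not the difference.** In the 40% example the arms differ by 14.5 cases in either window. Cases averted versus Control over D0-M20, planned for each arm (SAP 7.3.1.6), therefore keep the difference in expectation, with added noise. This is correct, but the labelled direct contrast is a ratio.
- **Little inferential weight.** SAP section 8 makes these comparisons descriptive, and power is low even without dilution. This limits the consequence but does not make the labelled estimate answer the aim.

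**Conclusion.** The gap is real. The two arms that isolate an early fourth dose are never compared directly from the month at which they diverge, and not at all in the exposed set. Over M2.5-M20 the relative effect on all episodes is diluted about 2.9-fold at constant incidence, and about 1.6- to 4.8-fold over the assumed range of k. The 14% shown for a true 40%, and the fall in expected z from 1.9 to 1.0, rest on 0.29 episodes per person-year, 250 per arm, Poisson counts and constant incidence.

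Two stronger readings do not hold. A reader might carry the threefold figure over to every window starting at Month 2.5. The longer windows have a different problem, because later doses in one or both arms are mixed in. A reader might also conclude that the Month 2.5 rows are wrong. They are legitimate whole-schedule summaries, but they do not measure the effect of giving the fourth dose early.

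**What to change.** In SAP Table 3 (exposed set) and Tables 4 and 6 (per protocol set), add R012-14 versus R012-20 for all episodes of clinical malaria:

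- **M14-M20:** fourth dose given versus not yet given.
- **M14-M26:** net effect of fourth-dose timing, to be labelled as net because R012-20 has the more recent dose from Month 20.

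Start time at risk at the Month 14 visit in both arms. The exposed-set rows matter because SAP 6.1.3 censors a child in the per protocol set at the first missed dose, and over M14-M20 only R012-14 has a fourth dose due. Report these rows as the descriptive answer to the early-fourth-dose aim, and keep the Month 2.5 windows as whole-schedule summaries.

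If M26-M38 and M38-M50 are added for this pair, label them as yearly doses versus a single fourth dose at Month 20. They would not isolate doses 5 and 6, because number of doses, time since the last dose and fourth-dose timing all differ.

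The cost is SAP wording and a few more runs of an existing model on data already collected. The arms share calendar time, so no seasonal adjustment is needed. The downside is a few more descriptive comparisons with low power: about 28% for a 30% reduction over M14-M20, before overdispersion.
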